4.3 Subsequent Daily Data Elements

Study Day One is the day of enrollment, beginning at the time of the first morphine or fentanyl administration in the PICU, and ending at 23:59 on that day. Each subsequent study day is defined as midnight (00:00) to 23:59. On each subsequent day (not study day one), the following data elements

Sedative Drugs and Components Sedative Drugs Answer Ketamine Yes or No Propofol Yes or No Chloral hydrate Yes or No Chlorpheniramine Yes or No Clonazepam Yes or No Diazepam Yes or No Droperidol Yes or No Etomidate Yes or No Yes or No Haloperidol Yes or No Hydroxyzine Methohexital Yes or No Yes or No Pentobarbital Phenobarbital Yes or No Promethazine Yes or No Yes or No Thiopental Yes or No Other (specify)

Table 1: Sedative agents.

Analgesic Drugs and	Components
Analgesic Drugs	Answer
Dexmedetomidine	Yes or No
Acetaminophen	Yes or No
Ibuprofen	Yes or No
Acetylsalicylic acid	Yes or No
Alfentanil	Yes or No
Buprenorphine	Yes or No
Butorphanol	Yes or No
Clonidine	Yes or No
Codeine	Yes or No
Dextromethorphan	Yes or No
Hydromorphone	Yes or No
Ketorolac	Yes or No
Meperidine	Yes or No
Methadone	Yes or No
Nalbuphine	Yes or No
Oxymorphone	Yes or No
Remifentanil	Yes or No
Tramadol	Yes or No
Other (specify)	Yes or No

Analgesic Drugs and Components

Table 2: Analgesic agents.

will be collected. This daily data collection will continue through Study Day 14, discontinuation of opioid therapy, death, or PICU discharge, whichever occurs earliest.

- 1. Date of data collection
- 2. Study day number (2 to 14)
- 3. Weight (kg) last measured or estimated weight
- 4. Was morphine or fentanyl infusion weaned (decreased) in the past 24 hours? (Yes or No)
- Was morphine or fentanyl infusion discontinued in the past 24 hours? (Yes or No) If yes to this question,
 - (a) Was morphine or fentanyl infusion restarted in the past 24 hours? (Yes or No)
 - (b) Were intermittent opioid doses started in the past 24 hours? (Yes or No)
- 6. Were muscle relaxants used in the past 24 hours? (Yes or No)
- 7. Were physical restraints used in the past 24 hours? (Yes or No)
- 8. Did inadvertent or unplanned dislodgement of an endotracheal tube occur in the past 24 hours? (Yes or No)
- 9. Did inadvertent or unplanned dislodgement of a central venous line occur in the past 24 hours? (Yes or No)
- 10. Did inadvertent or unplanned dislodgement of an arterial line occur in the past 24 hours? (Yes or No)
- 11. Did inadvertent or unplanned dislodgement of a thoracostomy tube occur in the past 24 hours? (Yes or No)
- 12. Did inadvertent or unplanned dislodgement of a peripheral venous line occur in the past 24 hours? (Yes or No)
- 13. Did inadvertent or unplanned dislodgement of a surgical drain occur in the past 24 hours? (Yes or No)

- 14. Did inadvertent or unplanned dislodgement of a urinary catheter occur in the past 24 hours? (Yes or No)
- 15. Total amount of morphine or fentanyl (mg/kg) given on this study day (total amounts of drug infusion plus additional boluses, from 00:00 to 23:59 hours)
- 16. Peak hourly dose of fentanyl or morphine given during the 24 hour day $(\mu g/kg/hr)$
- 17. If the subject is receiving midazolam by continuous IV infusion,
 - Number of hours that the midazolam drip was continued in the 24 hour day
 - Highest hourly dose (mg/kg) for midazolam given during the 24 hour day
- 18. If the subject is receiving intermittent lorazepam (by any route), total dose (mg/kg) given during the 24 hour day
- 19. Identify all other sedative (Table 1 on page 22) or analgesic (Table 2 on page 23) agents used during the first study day. If drug combinations are used, record all components of the drug combination.
- 20. Did the subject undergo a surgical procedure during this 24 hour period? Yes or no
- 21. If the subject did undergo a surgical procedure, select the category:
 - Cardiac surgery
 - Neurosurgery
 - Transplant surgery
 - Trauma surgery
 - Other surgery
- 22. Did the subject undergo any invasive procedures during this 24 hour period? Yes or no
- 23. If yes, how many procedures?
- 24. Did the subject have a creatinine > 1.2 during this 24 hour period? Yes or no

- 25. If yes, is the patient requiring dialysis or continuous renal replacement therapy? Yes or no
- 26. Did the subject have hepatic dysfunction associated with an INR > 2.0 during this 24 hour period? Yes or no

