3.4 Secondary Endpoints

Secondary endpoints for the MOTIF study are:

- 1. Average daily fentanyl or morphine dose within age groups (μ g/kg/day, all opioid drugs will be normalized to fentanyl equivalent doses using well-established opioid conversion ratios);
- 2. Peak fentanyl or morphine infusion rate (μ g/kg/hour, again all opioid drugs will be normalized to fentanyl equivalent doses using published opioid conversion ratios);
- 3. Total cumulative dose (mg/kg) and duration of fentanyl or morphine exposure (hours) during the stay, measured from the time of the first dose given after PICU admission and until study exit.

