- Chromosomal abnormality
- Diabetes
- Drug overdose (e.g. ingestion, toxicity)
- Gastroesophageal reflux
- Cardiovascular disease acquired
- Cardiovascular disease congenital
- HIV infection
- Hypoxic-ischemic encephalopathy of recent onset (acute, not static)
- Medical device malfunction
- Meningitis
- Pneumonia / bronchiolitis
- Seizures (includes complications of seizure therapy)
- Sepsis
- Shock
- Suicide attempt (includes intentional drug overdose)
- Transplant
- Trauma
- Other Diagnosis
- 17. Chronic Diagnoses (Select Multiple)
 - Bronchopulmonary dysplasia (BPD)
 - Cancer
 - Cerebral palsy
 - Chromosomal abnormality
 - Congenital heart disease
 - Diabetes
 - HIV infection
 - Hydrocephalus
 - Intraventricular hemorrhage (from perinatal period)
 - Mental retardation

- Meningomyelocele / spina bifida
- Short gut syndrome
- Static encephalopathy
- Transplant
- Other Diagnosis
- 18. Postoperative Surgical Status (Select one)
 - Not postoperative
 - Postoperative
 - Cardiac surgery
 - Neurosurgery
 - Transplant surgery
 - Trauma surgery
 - Other surgery
- 19. Date and time of start of mechanical ventilation via endotracheal tube or tracheostomy during current hospital admission
- 20. Date and time of first morphine or fentanyl dose in the PICU this is defined as Time 0 for the baseline opioid dose
- 21. Total amount of morphine or fentanyl (mg/kg) given before midnight on the first study day (total amounts of drug infusions plus additional boluses of morphine or fentanyl)
- 22. Total amount of midazolam or lorazepam (mg/kg) given before midnight on the first study day (total amounts of drug infusions plus additional boluses of midazolam or lorazepam.
- 23. Other sedative (Table 1 on the following page) or analgesic (Table 2 on page 23) agents used during the first study day. If drug combinations are used, record all components of the drug combination.

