4.4 Study Exit Data Elements

The following data will be recorded when the patient exits the study:

- 1. Study day of exit from study (1 to 14)
- 2. Time of exit from study (hh:mm)
- 3. Reason for exiting study:
 - (a) Reached end of study day 14
 - (b) Opioid therapy was discontinued
 - (c) Patient died
 - (d) Patient discharged from PICU
- 4. If reason for study exit was PICU discharge:
 - (a) Was patient on lorazepam at the time of PICU discharge? (Yes or No)
 - (b) Was patient on methadone at the time of PICU discharge? (Yes or No)
 - (c) Was patient on buprenorphine at the time of PICU discharge (Yes or No)
 - (d) Was patient on clonidine (for prevention or treatment of opioid withdrawal) at the time of PICU discharge (Yes or No)

5 Data Analysis

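### The peak opioid rate endpoint has no Day 1 measurement: its only data field is collected on Study Days 2 to 14

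*Protocol*

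**What the plan says.** Secondary endpoint 2 is the "Peak fentanyl or morphine infusion rate" in µg/kg/hour, after conversion to fentanyl equivalents (protocol sections 1.4, 3.4 and 5.2). None of these sections restricts it to particular study days. Endpoint 3, by contrast, states its window: first PICU dose to study exit.

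The matching data field is item 16 of section 4.3: "Peak hourly dose of fentanyl or morphine given during the 24 hour day". Section 4.3 opens its list with "On each subsequent day (not study day one), the following data elements", and its second item is "Study day number (2 to 14". For Day 1, section 4.2 (items 1 to 23) asks only for the "Total amount of morphine or fentanyl (mg/kg) given before midnight on the first study day". Section 4.4 allows exit on the first day: "Study day of exit from study (1 to 14".

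The section 4.3 list is also the only place for invasive procedures and their number (items 22 and 23, beginning "Did the subject undergo any invasive procedures during this 24 hour period"), raised creatinine and renal replacement (items 24 and 25), and hepatic dysfunction with raised INR (item 26).

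**The concern.** A named endpoint and the list of data meant to supply it do not match. If the protocol is followed as written, the database holds a peak over Days 2 to 14, while the endpoint as worded covers the whole of the observed therapy. Section 5.2 plans summaries, subgroup comparisons and regression models for the secondary endpoints, so the gap carries into planned analyses. It also changes who is described. Section 5.1 keeps children who die or are discharged in the primary denominator however short their stay, whereas a child who leaves on Day 1 cannot contribute to endpoint 2. A later analysis plan cannot repair this, because the collected fields do not contain the missing value.

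The same list structure leaves procedures and organ dysfunction without a first-day value, which limits their use as baseline covariates under Aim 2.

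**Working it through.** The plan attaches no figure to this point, so there is none to reproduce. The precision and power statements for 450 children concern outcome rates and do not depend on the peak field.

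**1. Item-by-item comparison of the two lists**

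| Element | Day 1 (section 4.2) | Days 2–14 (section 4.3) |
|---|---|---|
| Opioid total | item 21 | item 15 |
| Peak hourly opioid dose | none | item 16 |
| Invasive procedures, number | none | items 22–23 |
| Creatinine, renal replacement | none | items 24–25 |
| INR | none | item 26 |
| Muscle relaxants | none | item 6, with a 24-hour look-back |

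**2. Direction of the error.** The recorded peak is the maximum over Days 2–14; the endpoint as worded is the maximum over Days 1–14. A maximum over part of the days cannot exceed the maximum over all of them, so the recorded value is equal, too low, or (for a Day 1 exit) missing.

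**3. Which peaks are lost.** Day 2 starts at 00:00, so a rate still running at midnight is picked up by the Day 2 entry. What is lost is a rate reduced before midnight, a peak hour produced by a Day 1 bolus, and every Day 1 exit.

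**4. Can the Day 1 total stand in?** Total divided by hours gives a mean rate. Taking Day 1 as whole hours, the mean cannot exceed the highest hour, so it is only a lower bound for the peak hourly dose. Illustration with assumed values, not taken from the protocol: Day 1 lasts 12 h, with 4 µg/kg/h for 6 h and 2 µg/kg/h from then on.
- Day 1 total: 6 × 4 + 6 × 2 = 36 µg/kg; mean 36/12 = 3 µg/kg/h.
- True peak 4; recorded peak (Day 2 onward) 2; error (4 − 2)/4 = 50%.
- The Day 1 mean of 3 still falls short of 4.

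**5. How much observed time is unseen.** With Day 1 lasting h hours and L study days in all, the share is h / (h + 24 × (L − 1)). Assuming h = 12 (range 1 to 24):

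| Study days L | Share not covered |
|---|---|
| 1 | 100% |
| 2 | 33% (4–50%) |
| 4 | 14% (1–25%) |
| 7 | 8% (1–14%) |
| 14 | 4% (0.3–7%) |

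These are shares of time, not shares of children whose peak falls on Day 1. The protocol gives nothing from which to derive the latter.

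**6. Effect on associations with tolerance.** Section 4.1 defines tolerance on the daily total, boluses included, against the first 24 hours. Illustration, again with assumed values: 10 µg/kg in the first hour (before midnight), then 1 µg/kg/h for 23 h, gives a baseline of 10 + 23 = 33. A later steady 3 µg/kg/h gives 24 × 3 = 72, which exceeds 2 × 33 = 66. This child is tolerant, yet the highest hour was on Day 1 (10) and the recorded peak would be 3. Children who become tolerant can therefore be misrecorded too.

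**The case against.** The strongest reply is that little hangs on this. Peak rate is a secondary endpoint, its comparisons are exploratory, and the primary endpoint, precision and power are untouched. Only some Day 1 peaks are lost, because a rate that persists past midnight is recorded. Endpoint 2 states no window, so a sentence limiting it to Days 2–14 would remove the contradiction at no data cost. All of this stands. It lowers the weight of the point and offers a second remedy, but it does not supply the missing value or give Day 1 exits a peak.

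Three stronger readings are tempting, and the protocol does not support them.
- A reader might infer that Aim 2 lacks its baseline risk factors. Section 5.3 names age and gender, earlier opioid exposure and the age at which it began, length of opioid treatment, other drugs, and BMI. Section 4.2 collects source data for most of these at entry or on Day 1, along with PRISM III, diagnoses and postoperative status. Procedures, creatinine and INR are not named in section 5.3; they are further candidates.
- A reader might infer that Day 1 is the only day on which exposure surely precedes the outcome. The daily forms are dated, so for a child who first doubles on Day 5, exposures on Days 2–4 also come first.
- A reader might infer that muscle relaxants share the same gap. Item 6 reads "Were muscle relaxants used in the past 24 hours", so a Day 2 entry may reach back into Day 1, depending on when the form is completed. That does not help a Day 1 exit.

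**Conclusion.** The point holds as a mismatch between an endpoint and its data list. As the protocol stands, endpoint 2 cannot see Day 1: some peaks are understated, none is overstated, and Day 1 exits have no value. Procedures and renal and hepatic dysfunction have no Day 1 value and so cannot be used as baseline covariates.

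The overall size is unknown. Any number of affected children out of 450 would be an assumed share multiplied out, and the 50% error is an illustration that requires the reduction to occur before midnight. A reader might also infer that the error falls only on children who do not escalate, and so exaggerates links between peak rate and tolerance. The second illustration shows that tolerant children can be affected as well, so the direction of any bias in associations is not established. The correction is worth making because it is cheap and the analysis cannot recover the value from the fields as listed.

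**What to change.** Add the peak hourly fentanyl or morphine dose, from Time 0 to 23:59, to the Day 1 list in section 4.2, and derive endpoint 2 as the highest value over Days 1–14. In the same amendment, add items 22 to 26 for that period. Together these are six fields (one peak dose plus five items), entered once per child from the chart.

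If the Day 1 peak is not added, state wherever endpoint 2 is defined (sections 1.4, 3.4 and 5.2) that it covers Days 2–14 only and leaves out children who exit on Day 1.

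The cost is a protocol amendment, which section 4 already requires when data elements are added, and a little abstraction time. No patients or study procedures are added.

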4.1 Definitions

- **Analgesia:** the reduction or absence of the sense of pain without loss of consciousness, as reported by the patient, or judged clinically from the patients behavior or physiological responses
- **Sedation:** a pharmacologically produced depressed level of consciousness associated with reduced anxiety, stress, and excitement

- First study day: the period from the time that the initial dose of opioid is received in the PICU up to 23:59 hours on that day
- **Subsequent study days:** each calendar day starting at midnight (00:00 hours) and ending at 23:59 hours after the completion of the first study day (as defined above) during which the enrolled subject is an inpatient in the PICU
- **Ventilated day:** PICU day during any part of which the child requires mechanical ventilation support greater than chronic baseline requirements (out of the hospital), provided by endotracheal tube, tracheostomy, laryngeal or face mask
- **Invasive procedure:** Any procedure that breaks the skin barrier or mucous membrane barrier or involves the placement of a medical device (catheter, probe, electrode, drain, prosthetic, or anything else) into a body orifice or body cavity, other than momentary suctioning of the nose, mouth, endotracheal tube, or tracheostomy tube.
- **Opioid tolerance:** the need for increasing doses of opioid drugs in order to maintain the same pharmacological effects as those seen at the initiation of therapy. For the purposes of this study, opioid tolerance is clinically defined as a doubling of the total daily opioid dose (including infusions and boluses) as compared to the total daily opioid dose required during the first 24 hours of opioid therapy, in order to maintain adequate analgesia and sedation
- **Regularly scheduled opioids:** the subject receives opioid drugs daily, given at regularly scheduled intervals. In response to specific symptoms or signs, if the subject has received more than one opioid dose per day, on more than three days during the past week, or a total of more than six opioid doses in the past one week, then they will be considered equivalent to those receiving regularly scheduled opioids.
- **Chronic opioid treatment:** if the subject has received scheduled regular opioids (as defined above) for more than one week, they will be classified as receiving chronic opioid treatment.

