5.1 Analysis of Primary Endpoint

The primary endpoint for the MOTIF Study is the incidence of opioid tolerance among PICU patients receiving morphine or fentanyl infusions for analgesia and sedation. For the purposes of this study, opioid tolerance is defined by a doubling of the total daily opioid dose from the initiation of opioid therapy (0-24 hours) in the PICU. Tolerance can develop at any time during opioid therapy; therefore, as would be the case for an intention-to-treat analysis in a clinical trial, subjects who die or are discharged from the PICU will be included in the denominator for this endpoint, irrespective of number of days in PICU prior to death or discharge. We will examine the incidence of this endpoint 7 days and 14 days after initiation of morphine or fentanyl infusion therapy, in order to help determine appropriate parameters for future clinical trials. Rates of the primary endpoint will be summarized as proportions achieving tolerance by 7 days and by 14 days after opioid therapy initiation, together with appropriate confidence intervals.

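### The daily opioid totals do not separate operating-room doses, so read literally an operation after Day 1 can create a tolerance event and one on Day 1 can hide it

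*Protocol*

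**What the plan says.** The primary endpoint in 5.1 (also 1.3 and 3.3) states that "opioid tolerance is defined by a doubling of the total daily opioid dose from the initiation of opioid therapy (0-24 hours) in the PICU". Section 5.1 adds that tolerance may develop at any point in therapy. It gives no rule requiring a sustained rise and no rule for days with an operation.

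Section 4.1 gives the construct and its working form. The construct is "the need for increasing doses of opioid drugs in order to maintain the same pharmacological effects as those seen at the initiation of therapy". The working form is a "doubling of the total daily opioid dose (including infusions and boluses", compared with the first 24 hours, and required "in order to maintain adequate analgesia and sedation".

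The doses come from two fields:

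- **Day 1 (4.2).** Item 20 fixes the start: "Date and time of first morphine or fentanyl dose in the PICU this is defined as Time 0 for the baseline opioid dose". Item 21 then takes the amount "given before midnight on the first study day (total amounts of drug infusions plus additional boluses of morphine or fentanyl".
- **Days 2-14 (4.3).** Item 15 takes the amount "given on this study day (total amounts of drug infusion plus additional boluses, from 00:00 to 23:59 hours".

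Item 20 of 4.3 asks: "Did the subject undergo a surgical procedure during this 24 hour period? Yes or no". Item 21 of 4.3 asks for the category of surgery. No field records the dose given during the operation.

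**The concern.** The definition in 4.1 is about needing more drug for the same effect. Opioid given as part of an anaesthetic serves a different effect. The protocol expects operations during the stay, because it asks about them every day, yet neither the dose fields nor the scoring rule separates that opioid from the dose given for analgesia and sedation in the PICU.

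The primary incidence (Aim 1) is at stake. A child whose PICU regimen has not changed could be counted as tolerant because of one operative day. A child operated on during Day 1 after Time 0 could carry an inflated baseline and be counted as not tolerant. Under the same literal recording, the peak hourly dose (4.3, item 16) and the cumulative-dose secondary endpoint would also take in these doses.

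**Working it through.** **1. The plan's own figure.** Inputs from 5.4: n = 450, and a tolerance rate of at least 25% (assumed there for model fitting). The 95% half-width is 1.96 × √(p(1−p)/450). This is 4.00 points at p = 0.25 or 0.75 and 4.62 points at p = 0.50. The stated 4-5% therefore reproduces for rates from 25% to 75% and is a fair yardstick.

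**2. The fields side by side.**

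| | Day 1 (4.2, item 21) | Days 2-14 (4.3, item 15) |
|---|---|---|
| Starts | first PICU dose (Time 0) | 00:00 |
| Ends | midnight | 23:59 |
| Content | infusions plus boluses | infusion plus boluses |
| Limit by place or purpose | none | none |
| Same-day surgery flag | none | item 20 |
| Separate operating-room dose | none | none |

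Only the starting time is tied to the PICU. After that, both fields are equally open. The purpose condition in 4.1 is not carried into either field.

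**3. How much operating-room opioid creates an event after Day 1.** Let B be the baseline daily total and let the PICU dose on the operative day be r × B. The event needs a total of at least 2B, so the operating-room dose needed is (2 − r) × B:

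- r = 1 (unchanged regimen): 1.0 × B
- r = 1.5: 0.5 × B
- r = 1.75: 0.25 × B

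One such day is enough.

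**4. How Day 1 works the other way.** If an operation after Time 0 on Day 1 adds f × B to the baseline, the threshold becomes 2(1 + f) × B in terms of the PICU-only baseline. With f = 0.5 the child must reach 3 × B, and with f = 1 it must reach 4 × B.

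**5. Size of the upward part.** The documents give neither a rate of operations after Day 1 nor an operating-room dose, so every input here except p is an assumption. Let p be the rate without operating-room doses, s the share of otherwise non-tolerant children operated on after Day 1, and q the chance that the operative day then reaches twice baseline. The shift is (1 − p) × s × q. At p = 0.25:

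| s | q | shift (points) | children of 450 |
|---|---|---|---|
| 5% | 0.10 | 0.75 × 0.05 × 0.10 = 0.4 | 1.7 |
| 5% | 0.25 | 0.75 × 0.05 × 0.25 = 0.9 | 4.2 |
| 10% | 0.50 | 0.75 × 0.10 × 0.50 = 3.75 | 16.9 |
| 20% | 0.50 | 0.75 × 0.20 × 0.50 = 7.5 | 33.8 |
| 20% | 1.00 | 0.75 × 0.20 × 1.00 = 15.0 | 67.5 |

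The shift equals the 4.0-point half-width when s × q = 0.04/0.75 = 0.053, that is, when about 1 in 19 otherwise non-tolerant children is miscounted (18 of 337.5). The Day 1 effect would be set against this, but nothing in the documents allows it to be sized.

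**The case against.** The strongest reply is that 4.1 already settles the matter. The doubling must be needed for adequate analgesia and sedation, and the endpoint population is described as receiving infusions for that purpose, so anaesthetic doses are outside the definition. Which chart entries feed a field can be settled in form instructions, and the scoring of operative days can be left to an analysis plan that is not shown. Part of this stands: the protocol never mentions operating-room doses, and they enter only because nothing excludes them. But the condition in 4.1 is applied by no data element. An analysis plan could drop days with item 20 = Yes, but it could not subtract a dose never recorded separately, and Day 1 has no such flag. Section 4 requires a protocol amendment to add a data element.

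Three stronger readings are tempting, and the documents do not support them:

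- **That the baseline is PICU-only, so the error always inflates incidence.** Only Time 0 is tied to the PICU. Item 21 is as unrestricted as item 15, and Day 1 surgery biases downwards.
- **That the error is known to match or exceed the stated precision.** This rests wholly on assumed inputs. Only morphine and fentanyl enter items 21 and 15. Remifentanil and alfentanil are recorded yes/no, so an anaesthetic using only those adds nothing.
- **That surgery will emerge as a spurious risk factor.** Surgery and diagnosis are not among the factors named in 5.3, and those analyses are exploratory.

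It is also true that extra analgesia on the days after an operation would still count under the change proposed here.

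**Conclusion.** The point holds as a mismatch between the definition in 4.1 and the fields and scoring rule meant to carry it out. Literal recording can turn one operative day after Day 1 into a tolerance event and can mask tolerance when the operation falls on Day 1 after Time 0.

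The size is unknown. With p = 25% from 5.4 and assumed values of 5-20% for s and 0.10-1 for q, the upward shift runs from 0.4 to 15 points, before any offset from Day 1. Enrolling more children would not remove it. It should be fixed before data collection because the separate dose cannot be recovered from the study data afterwards. A reader might infer that the primary result is unusable without the change. The documents do not show that, since the low end of the range lies well inside the stated precision.

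**What to change.** - Word item 21 (4.2) and item 15 (4.3) alike, so that both cover morphine or fentanyl given for PICU analgesia and sedation.
- Record operating-room morphine or fentanyl in a separate field on surgical days. Put it on the Day 1 form too, because 4.2 has no same-day surgery question.
- In 5.1, score the primary endpoint on the PICU-only total, for the baseline and for later days.
- Report two sensitivity results: the all-dose version (PICU total plus the new field), and a version that leaves out days with item 20 = Yes.

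The cost is one extra field on surgical days, the amendment that section 4 requires for a new data element, and a sentence or two in 5.1.

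### As written, the Day 2–14 form does not record use of the Table 1 and Table 2 sedatives and analgesics, and midazolam is measured on a different scale after Day 1

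*Protocol*

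**What the plan says.** Section 4.2 lists the study entry and Day 1 items. Item 23 asks for other Table 1 sedatives and Table 2 analgesics: "agents used during the first study day. If drug combinations are used, record all components of the drug combination". Item 22 asks for a benzodiazepine amount, "Total amount of midazolam or lorazepam (mg/kg) given before midnight on the first study day", and specifies that infusions and boluses both count.

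Section 4.3 covers the later days, numbered 2 to 14. Its lead-in is "On each subsequent day (not study day one), the following data elements". Within that list, item 19 reads "Identify all other sedative (Table 1 on page 22) or analgesic (Table 2 on page 23) agents used during the first study day". Item 17 applies only if midazolam runs as a continuous infusion. It takes the hours of infusion and the "Highest hourly dose (mg/kg) for midazolam given during the 24 hour day". Item 18 takes a daily total for lorazepam, but only if it is given intermittently.

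Use of concomitant medications is a named explanatory factor (sections 1.5, 3.5 and 5.3). Section 5.3 also plans exploratory mixed models on the daily data, to describe opioid dosing over time and the factors associated with different patterns.

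**The concern.** Item 19 stands in a list that excludes Day 1 but asks about Day 1. A form built to the letter would repeat a question already answered and would not ask about these agents on the later days. Tolerance is defined in section 4.1 by a doubling of opioid dose needed to keep analgesia and sedation adequate, and section 2.1 describes synergy between analgesics and sedatives as established. A change in co-sedation after Day 1 is therefore a plausible alternative explanation for a change in opioid dose, and the risk-factor analysis needs to see it.

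The midazolam items raise a second problem, which does not depend on how item 19 is read. The Day 1 measure and the later measure are different quantities, and neither can be converted into the other.

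**Working it through.** The protocol gives no figure to reproduce. The check sets the Day 1 and later items side by side and counts what falls out.

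**Item 19, read literally**

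- Table 1 names 15 sedatives and Table 2 names 18 analgesics: 15 + 18 = 33, plus one free-text field in each table.
- The list includes ketamine, propofol, dexmedetomidine, clonidine and opioids other than morphine and fentanyl, such as methadone, hydromorphone and remifentanil.
- A child followed for D study days has D − 1 days without these data. For D = 14 this is 13/14 = 93%; for D = 7 it is 6/7 = 86%; for D = 2 it is 1/2 = 50%.

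**What is collected on Days 2–14**

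| Exposure | Day 1 (section 4.2) | Days 2–14 (section 4.3) |
|---|---|---|
| Table 1 and Table 2 agents | Yes/no (item 23) | Not recorded if item 19 is followed as written |
| Midazolam infusion | In the total, mg/kg (item 22) | Hours and highest hourly dose (item 17) |
| Midazolam boluses | In the total (item 22) | No dedicated item |
| Lorazepam, intermittent | In the total (item 22) | Daily total, any route (item 18) |
| Lorazepam, continuous | In the total (item 22) | No dedicated item |
| Muscle relaxants | – | Yes/no (item 6) |
| Morphine or fentanyl | Total (item 21) | Daily total (item 15) |

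**Midazolam on one scale**

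Let H be the recorded infusion hours and P the highest hourly dose. The infused amount cannot exceed H × P, and equals it only if the rate stayed at its peak throughout. If the peak was an infusion rate held for one hour, the amount is at least P. For H = 24 the infused dose therefore lies anywhere from P to 24P. Boluses come on top, and a child who receives boluses alone does not trigger item 17 at all. The Day 1 total has no counterpart on later days.

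Midazolam and lorazepam are in neither table. Even with item 19 corrected, bolus midazolam or infused lorazepam could appear only under a free-text field, as yes/no without a dose.

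**Whether other items fill the gap**

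- Item 5(b) of section 4.3 asks whether intermittent opioids were started, but only after an infusion was discontinued, and it does not name the drug.
- Section 4.4 asks about lorazepam, methadone, buprenorphine and clonidine, but only at the moment of PICU discharge.

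Neither replaces daily recording.

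**The case against.** The strongest reply is that item 19 is plainly a carry-over. The section heading and lead-in concern later days, the neighbouring items refer to the current day, and the second sentence of item 19 repeats Day 1 item 23. A sensible form builder would ask about the current day, and the electronic form is not shown, so 93% is the result of a literal reading and not a prediction. This stands as a description of how the error arose: it is a wording slip, not a design choice. It does not remove the need to correct it. Section 4 presents this list as the data elements to be collected, requires an amendment to add or drop any, and lets only choice sets change freely. The time window is part of the element.

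A reader might infer that no concomitant exposure is captured after Day 1. The table above shows otherwise: muscle relaxants, midazolam infusion hours and peak, and intermittent lorazepam totals are all collected.

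A reader might also infer that the primary endpoint is damaged. The morphine and fentanyl totals come from item 21 of section 4.2 and item 15 of section 4.3, and do not depend on item 19.

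On midazolam, it is fair to say that hours and peak rate are a usable exposure measure and that the protocol plans no analysis of daily benzodiazepine dose. That limits the consequence but does not make the two measures comparable. Nor does the text establish that midazolam and lorazepam are added into a single Day 1 figure. Item 22 is worded like the morphine or fentanyl item, and the form might hold them apart.

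**Conclusion.** The point holds in two limited parts.

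1. Item 19 carries the Day 1 window into the Day 2–14 list. Followed as written, it leaves 33 named agents and two free-text fields unrecorded on up to 13 of 14 days. This rests on the literal text; if the form was built to ask about the current day, the loss does not occur and only the protocol wording is wrong.
2. Midazolam is a total dose on Day 1 but hours and peak rate later, with no dedicated item for midazolam boluses or continuous lorazepam. A daily midazolam dose cannot be derived on one scale. This holds on any reading of item 19.

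The analyses affected are the Aim 2 risk-factor models and the repeated-measures analyses, which section 5.3 describes as exploratory. The documents do not support calling co-sedation the main explanation for opioid dose change. They support calling it a plausible one that the planned analyses should be able to examine.

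**What to change.** Reword item 19 of section 4.3 to ask for agents used during this study day, 00:00 to 23:59. On Day 1 and on every later day, record total midazolam and total lorazepam (infusion plus boluses, mg/kg) as two separate items. Infusion hours and peak rate can stay alongside.

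The cost is a change of wording and one or two extra fields, taken from the medication record that sites already use for the opioid totals. Under section 4's own rule the added fields need a protocol amendment, and item 19 can be corrected in the same one. This is best done before the electronic form is final, because it involves no change to patient care and late correction would mean going back to charts. Correcting item 19 restores yes/no use of the listed agents. It does not supply their doses, since both tables are yes/no.
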